9.0 Data Reporting Conventions

All listings will be ordered by phase, group (for Phase II only) and INXN-1001 actual initial dose (5mg QD, 20mg QD, 100mg QD, 160mg QD in Phase I; 160mg QD, 160mg QOD, 120mg QOD, 80mg QOD in Phase II) and patient number. Listings will present all available data.

Unless otherwise stated, data will be summarized by phase and dose cohort based on the actual dose of INXN-1001 received on Cycle 1 Day 1. For Phase II, data will be summarized based on group; additionally for Group 2, data will be presented by dose cohort. The combined data for each phase will also be summarized as an 'Overall' column.

No inferential statistics will be performed.

9.1 Descriptive Statistics

Unless otherwise stated, all continuous parameters will be summarized using standard summary statistics as appropriate (n, mean, standard deviation, minimum, median and maximum). Summary statistics for categorical variables will include frequency counts and percentages.

In the presentation of descriptive summary statistics, the minimum and maximum will be presented to the same number of decimal places as the variable being reported. The mean and median will be reported to one extra decimal place; the standard deviation (SD) to two extra decimal places.

Frequency counts will be provided for categorical variables (e.g., gender). Unless otherwise stated, this will consist of the number of patients in a particular category and the percentage of total patients for the treatment (Phase I)/treatment regimen (Phase II only) in each, presented to one decimal place. Categorical data will be summarized using counts and percentages based on non-missing values.

Zero counts will be presented as '0' lined up on the decimal place.

Tables will have a footnote of the form "Table XX is supported by Listing XX".

Analyses will be undertaken using the validated statistical software Statistical Analysis System (SAS) version 9.3 or later.

9.2 Baseline

Unless otherwise specified, baseline is the last observation before the first study drug administration.

9.3 Missing Data

If there are partial dates which require imputation, the day and/or month and/or year will be imputed in a conservative manner i.e. for the start dates, if only the day is missing, it will be imputed with the first day of the month. If the month is also missing, it will be imputed with the 1st January. For the end dates, if only the day is missing, it will be imputed with the last day of the month and if the month is also missing, it will be imputed with the 31st December. In addition, imputed dates for data that is

expected to occur on study will be modified to be consistent with appropriate known study visit dates.

Missing values for safety measures at Baseline such as laboratory data, vital signs and electrocardiogram (ECG) data will be substituted by values from the screening visit, where available.

No further imputations for missing data will be made.

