12.2 Adverse Events

Adverse events will be coded according to MedDRA dictionary version 10.

Symptoms and signs of exacerbation or worsening of the patient's primary disease will be captured as AEs.

A treatment emergent adverse event (TEAE) is defined as an AE occurring during or after administration of first dose of study drug, or any event after the first dose of study drug considered study drug-related regardless of event start date, or any worsening in intensity or event considered drug related by the investigator of a pre-existing medical condition/AE with onset after the start of study drug, and until Post-Treatment Safety Assessment visit (28 days after the last INXN-1001 dose per patient). AEs with unknown start date/time will be assumed to be treatment-emergent

unless the end date/time is known to be before start of study drug. AEs with onset after the completion of screening but prior to the start of study drug will be considered non-treatment emergent.

An overall AE summary will be presented for all AEs and the pre-defined subsets of events below:

- Any AEs
- Any TEAE events
- Any drug-related AEs
- Any CTC Grade 3 or greater AEs
- Any CTC Grade 3 or greater drug-related AEs
- Any AEs leading to death
- Any drug-related AEs leading to death
- Any serious AEs (SAEs)
- Any drug-related serious AEs
- Any AEs leading to discontinuation
- Any drug-related AEs leading to discontinuation
- Any dose limiting toxicities

Related is defined as 'possibly related' or 'related' to treatment in the opinion of the investigator.

Both number of events and number of patients will be tabulated. For patients, percentages will be calculated from the total number of patients per INXN-1001 dose cohort in each phase and group (for phase II only).

Summaries of TEAEs, drug-related adverse events, SAEs, drug-related SAEs, AEs with CTC grade ≥ 3 , drug-related AEs with CTC grade ≥ 3 and AEs leading to discontinuation will be tabulated by MedDRA System Organ Class (SOC) and specific AE preferred Term (PT) sorted by decreasing frequency within SOC. Both number of events and number of patients will be tabulated. For patients, percentages will be calculated from the total number of patients per INXN-1001 dose group.

All AEs, TEAEs, SAEs, drug-related adverse events, adverse events leading to discontinuation of study medication and adverse events leading to death will be listed.

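### The SAP's rule for partial start dates can place an on-treatment adverse event before first dose, and the SAP does not say that its treatment-emergent default overrides this

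*SAP*

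**What the plan says.** SAP 9.3 (Missing Data) sets one rule for all partial start dates: "if only the day is missing, it will be imputed with the first day of the month". It continues: "If the month is also missing, it will be imputed with the 1st January". Partial end dates go the other way: "For the end dates, if only the day is missing, it will be imputed with the last day of the month". The same paragraph adds that imputed dates for data "expected to occur on study will be modified to be consistent with appropriate known study visit dates".

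SAP 12.2 (Adverse Events) then decides treatment-emergent status. The basic definition needs occurrence during or after the first dose. Three further statements matter:

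- The default: "AEs with unknown start date/time will be assumed to be treatment-emergent", with one exception, "unless the end date/time is known to be before start of study drug".
- The exclusion: "AEs with onset after the completion of screening but prior to the start of study drug will be considered non-treatment emergent".
- The drug-related limb of the definition: "or any event after the first dose of study drug considered study drug-related regardless of event start date". Protocol 10.3.2 has the same limb.

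The SAP does not say whether the default is applied before or after the 9.3 imputation, or whether a date with a known month or year counts as unknown.

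**The concern.** Imputing to the earliest possible date is conservative for a duration. It is not conservative for deciding whether an AE began on treatment, because the earliest date is the one most likely to precede first dose. An AE that began after first dose in the same calendar month, recorded without its day, is dated to the 1st. Unless dosing was also on the 1st, that date is before treatment.

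Safety and tolerability is the primary objective (Protocol 6.1, SAP 3.1). Protocol Appendix 3 says that most toxicity has been seen from the first injection through Cycle 2, so onset soon after first dose is where classification matters. The cohorts are small: SAP 1.0 gives 3, 3, 3 and 4 patients in Phase I and 4, 4, 3 and 2 in Phase II. Two programmers could each follow the SAP and produce different TEAE tables.

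**Working it through.** The plan states no figure on this point, so there is none to reproduce. The check has two parts: how often the 9.3 rule would place an on-treatment onset before first dose, and whether other text prevents it.

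**1. The 9.3 rule taken alone**

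Inputs: the rules for a missing day and a missing month (SAP 9.3), and cycle lengths of 21 and 28 days (Protocol 6.2.1). A 7-day window is added for early onsets. Assumptions: first dose is equally likely on each of the 1,461 days of a four-year span (48 months), and onset is uniform over the L days starting at first dose.

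*Day missing.* The imputed date precedes first dose exactly when onset falls in the calendar month of first dose and first dose is not on the 1st. In each month, L(L − 1)/2 of the pairs of first-dose day and onset day spill into the next month, and L pairs have first dose on the 1st. The share imputed before first dose is therefore

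1 − 48 × [L(L − 1)/2 + L] / (1,461 × L) = 1 − 24(L + 1)/1,461.

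*Month also missing.* The same argument with 4 years in place of 48 months gives 1 − 2(L + 1)/1,461.

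| Onset window | Day missing | Month also missing |
|---|---|---|
| 7 days | 1 − 192/1,461 = 86.9% | 1 − 16/1,461 = 98.9% |
| 21 days | 1 − 528/1,461 = 63.9% | 1 − 44/1,461 = 97.0% |
| 28 days | 1 − 696/1,461 = 52.4% | 1 − 58/1,461 = 96.0% |

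A direct enumeration of all pairs (10,227, 30,681 and 40,908 for the three windows) gives the same percentages.

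**2. The rule with the rest of the SAP**

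*The 12.2 default.* If an unknown start date includes a partial one, and the default comes before imputation, no event is lost: 0 of 30,681 and 0 of 40,908. An event that starts on or after first dose cannot have ended before it, so the sole exception never applies. If unknown means wholly missing, a partial date goes through 9.3 and the percentages above apply. The wording leaves both readings open. SAP 9.3 speaks of partial dates and 12.2 of unknown ones. For medications, SAP 10.5 uses a broader trigger, treating a drug as concomitant whenever its dates leave the period unclear. The AE rule has no such wording.

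*The visit-date adjustment.* It does not name first dose. AEs are recorded from informed consent (Protocol 8.4.2.6 and 9.3), so an imputed date between consent and first dose already agrees with the visit record and nothing moves it forward.

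*Month-end imputation of end dates.* This does not help, because the pre-dose exclusion in 12.2 turns on onset.

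*The drug-related limb.* This keeps related and possibly related events whatever their start date. Only events judged unrelated remain exposed.

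**3. Where it would show**

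Affected: the TEAE row of the overall summary, Table 14.3.2.3, and the listings titled treatment-emergent (16.2.7.2 to 16.2.7.6, apart from drug-related events). Not affected: the tables of all AEs (14.3.2.2), SAEs (14.3.2.5), Grade 3 or greater AEs (14.3.2.7) and AEs leading to discontinuation (14.3.2.9), none of which is titled treatment-emergent, and Listing 16.2.7.1 of all AEs.

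**The case against.** The strongest reply is that 12.2 is the AE-specific section, that 9.3 covers only dates needing imputation, and that the specific default should govern. On that reading nothing is lost. It is a fair reading and may be what was intended, but the SAP does not state it.

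The rest of the reply limits the point, and it stands. Drug-related events are protected. The main AE, SAE and Grade 3+ tables do not depend on treatment-emergent status. Protocol 9.3 requires the date of onset to be recorded, and visits are frequent early in each cycle, so partial dates may be few. Dates with only the year known are improbable for AEs collected prospectively. Cycle 2 starts 21 or 28 days after first dose, so its events usually fall in a later month, where a missing day cannot move them before first dose.

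A reader might infer that the SAP does drop Cycle 1 events, or that about 97% of them are at risk. The documents support neither. The first takes one reading of an ambiguity as settled. The second is 29/30, the chance in a 30-day month that first dose is not on the 1st. It applies only to onsets in the month of first dose, not to all Cycle 1 onsets.

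**Conclusion.** The point holds as a gap in the stated rules. The imputation rule works against the safety classification, and neither the default nor the visit-date adjustment clearly stops it. If 9.3 governs, about 87%, 64% and 52% of day-missing onsets in 7-, 21- and 28-day windows would be imputed before first dose, given uniform onset and first-dose dates. If the 12.2 default governs, the figure is zero. These are shares of AEs with a missing day. The documents do not say how many there are, so no number of lost events can be given.

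The exposure is confined to events not judged drug-related and to the treatment-emergent outputs. Within those, one patient is 1/4 to 1/2 of a cohort of 4 to 2, or 25 to 50 percentage points, but only where the misdated event is that patient's only one in the row. This is worth correcting because it touches the primary objective and costs little. It is not evidence that toxicity is being hidden.

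**What to change.** Add one sentence to SAP 9.3 and refer to it from 12.2, for AE start dates only. If the known parts of the date are compatible with onset on or after first dose, and the end date is not known to be before first dose, the start date is imputed as the later of (a) the first of the recorded month, or 1 January of the recorded year, and (b) the date of first dose. The event is then classed as treatment-emergent.

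No change is needed for medications. SAP 10.5 defines prior use by stop date and already assumes concomitant use when the dates are unclear.

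The cost is the sentence and a small programming change, made before the tables are run. TEAE counts may rise slightly, because some events that truly began before first dose in that month or year will be counted as treatment-emergent. For a safety table that is the conservative direction.

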10.0 Patient Disposition and Baseline Information

10.1 Patient Disposition

Study completion/discontinuation details, time to discontinuation, date of first dose of study treatment, informed consent, inclusion/exclusion criteria including protocol amendment recruited under, eligibility, protocol deviations and population allocation will be listed.

Time to discontinuation (days) = (date of last contact) - (date of first dose of INXN-1001 or INXN-2001, whichever is earliest) +1 day

The number of patients screened and treated, prematurely discontinued/completed the study and primary reason for study treatment completion/discontinuation will be tabulated.

The number and percentage of patients in each analysis population (i.e. SAF, ACEV) will be tabulated.

10.2 Demographic Characteristics

Demographic parameters (including date of birth, age, sex, ethnicity, race, height (cm), weight (kg) and BMI (kg/m²)), BRAF status and mutation type will be listed. Demographics will be tabulated using frequency counts and descriptive statistics as appropriate.

Age will be derived as follows:

```
Age=floor ((intck('month',birth,screen) - (day(screen) < day(birth)) / 12)
```

Conversions for height and weight are as follows:

Height (cm) = Height (inches) x 2.54

Weight (kg) = Weight (lb) x 0.4536

10.3 Medical History

Details of medical/surgical history will be listed including start and stop dates, and whether medication currently used.

Medical histories will be coded according to the MedDRA dictionary version 10. A summary of medical histories and number of patients with a medical history will be presented by System Organ Class and Preferred Term.

Tables will be presented by phase only.

10.4 Oncology History and Prior Cancer Therapy

Details of oncology history will be listed including tumor type, diagnosis date, current disease status, staging (TNM, Tumor – Tis, Ta, Tx; Node – N0, N1, N2; Metastasis - M0, M1, M2) and staging.

Time from first diagnosis to date of screening, current disease status and staging (TNM, T – Tis, Ta, Tx; N – N0, N1, N2; M - M0, M1, M2) will be tabulated.

Time from first diagnosis will be derived as follows:

Time from first diagnosis = Date of screening – Date of first diagnosis + 1 day.

Oncology histories will be coded according to the MedDRA dictionary version 10. A summary of oncology histories and number of patients with an oncology history will be presented by System Organ Class and Preferred Term.

Prior cancer treatment information will be tabulated. This will include the number of previous treatments received and therapy type.

Tables will be presented by phase only.

10.5 Prior and Concomitant Medication

Medications will be classified according to whether they were being taken pre-study (prior) and/or during the study (concomitant). Prior medications are any that were being taken prior to the first dose of study medication (medication stop date prior to the first dose of study medication). Concomitant medications are any that were being taken on or after the first dose of study medication. If the start and stop dates of the medications do not clearly define the period(s) during which a medication was taken, it will be assumed to be a concomitant medication.

Prior and concomitant medications recorded during the study will be coded using World Health Organization (WHO)-Drug dictionary Q3 2009. Details of prior and concomitant medication will be listed separately.

Prior and concomitant medications will be summarized by preferred term and Anatomical Therapeutic Chemical (ATC) level 2 term.

Tables will be presented by phase only.

11.0 Efficacy

Patients with measurable disease will have tumor dimensions measured according to Response Evaluation Criteria in Solid Tumors (RECIST) version 1.1 at Screening

and at the each cycle up to cycle 6 during the study and 8-10 weeks after follow-up if the patient is without objective evidence of disease progression at the Follow-Up Tumor Assessment visit. The investigator will evaluate each patient for response to therapy according to RECIST v1.1 guidelines. For each patient, disease sites are to be assessed throughout the study using the same method(s) of assessment used at screening.

Additional assessment of anti-tumor activity will be explored based on total measurable burden.

Immunological and biological markers of response will include examinations of tumor biopsy samples, cytokine levels, peripheral blood mononuclear cells (PBMC) and antibody responses.

All summaries will be performed on the ACEV population and based on the dose of INXN-1001 received.

11.1 Efficacy Endpoints

Details of target lesions, non-target lesions and new lesions will be listed.

11.1.1 Objective Response Rate

Individual overall tumor responses (Complete Response (CR), Partial Response (PR), Stable Disease (SD), Progressive Disease (PD) and Unevaluable) as measured by RECIST v1.1 guidelines will be listed. The objective response is defined as a complete response or a partial response. Non-responders are those either with stable or progressive disease. Those subjects that cannot be assessed will be treated as non-responders. Objective response will be listed as a Yes/No response for each subject. The objective response rate will not be tabulated.

The best overall response (BOR) will be listed for each subject and tabulated.

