5.5 RATIONALE FOR STUDY DESIGN AND DOSE SELECTION

The objectives of this Phase I/II clinical trial are to assess the safety, objective response rate, and immunological and biological effects of intratumoral injections of INXN-2001 in combination with escalating dose levels of oral INXN-1001. The dose escalation portion of the study (Phase I) uses a standard 3+3 design commonly used in Phase I studies of investigational anticancer therapies. To provide an opportunity to monitor the safety of the combination therapy, there will be at least 7 days between the initiation of treatment for the sentinel (first) subject and additional subjects in all cohorts during the dose escalation stage of the study. Phase II will be enrolled (approximately 15 subjects) at or below the MTD and using two groups. One group will receive an INXN-1001 daily for 7 days dosing regimen, and the other group will receive an every other day dosing regimen for 14 days to compare tolerability of INXN-1001 at the 160-mg dose.

Phase I: In each of six 21-day cycles, the subjects will receive one intratumoral injection of INXN-2001 in combination with 7 oral daily doses of INXN-1001.

Phase II, Group 1: In each of six 21-day cycles, the subjects will receive one intratumoral injection of INXN-2001 in combination with 7 oral daily doses of INXN-1001.

Phase II, Group 2: In each of six 28-day cycles, the subjects will receive one intratumoral injection of INXN-2001 in combination with 7 oral doses of INXN-1001 administered every other day for 14 days.

The INXN-1001 dose levels to be studied (5 to 160 mg/day) are within the range of doses administered in previous human clinical trials [REDACTED] and are expected to provide plasma levels that are biologically effective for [REDACTED] activation. Although good safety and tolerability is expected based on previous clinical experience, rigorous safety monitoring during the course of this study will be performed by the Safety Review Committee (SRC).

In all treatment cycles throughout the study, the INXN-2001 dose will be fixed [REDACTED] dose. This dose was selected based on: (i) preclinical studies that indicated that this would be within an effective range, and (ii) previous clinical trials of administered adenoviral vectors [REDACTED]

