10.3.3 Efficacy Analyses

The Activity Evaluable Population will be used for the analyses of efficacy data based on the dose of INXN-1001 received.

Following completion of the study, best response will be determined for each subject in accordance with RECIST v.1.1 guidelines and the objective response rate presented for each dose cohort. Progression-free survival and durability of response will be determined using Kaplan-Meier methodology.

As a supplement to the standard RECIST v1.1 guidelines established to evaluate anti-tumor responses to chemotherapeutic agents, the sponsor will be analyzing anti-tumor response by assessing total tumor burden over time. Please refer to [Appendix 4](#) for a description of “immune-related Response Criteria” (irRC).

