2.0 Study Rationale

This study was designed to assess the safety, objective response rate and immunological and biological effects of intratumoral injections of INXN-2001 in combination with escalating dose levels of oral INXN-1001.

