3.2 Secondary Objectives

The following secondary objectives were to be evaluated in the trial:

- To inform the selection of an INXN-1001 dose(s) and regimen for further study in combination with INXN-2001.

- To assess preliminary anti-tumor activity according to Response Evaluation Criteria In Solid Tumors (RECIST) 1.1 criteria.
- To assess anti-tumor response based on total measurable tumor burden.
- To evaluate the immunological effect of study treatment in terms of cellular and humoral immune responses, as well as other biological activities in the injected tumor(s), tumor-involved draining lymph nodes (if accessible) and in the peripheral circulation.
- To evaluate the extent of the uptake of INXN-2001 into tumor cells and tumor-infiltrating immune cells, and to assess adenoviral vector shedding in body fluids.
- To assess the pharmacokinetics (PK) of INXN-1001 in patients with unresectable stage III or IV melanoma.

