4.0 Study Design

4.1 Endpoints

Safety Evaluations

Safety parameters were to include serious adverse events (SAEs), adverse events (AEs), physical examinations, electrocardiograms (ECGs), vital signs, clinical laboratory evaluations, medical history, and prior/concomitant medications.

Efficacy Evaluations

Efficacy was to be evaluated as the objective tumor response according to RECIST v1.1 guidelines. Additional assessment of anti-tumor activity was to be explored based on total measurable tumor burden.

Pharmacodynamic Evaluation

Immunological and biological markers of response were to include examinations of tumor biopsy samples, cytokine levels, peripheral blood mononuclear cells (PBMC) and antibody responses.

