6.0 Patient Disposition

6.1 Sample Size

No formal sample-size estimation was performed.

Thirteen patients were treated in Phase I and 13 patients were treated in Phase II.

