14.0 Changes to Planned Methodology

The following changes will be made to the planned analysis based on the final number of enrolled subjects:

Section 10.3.3 of the Protocol states that following completion of the study, best response will be determined for each subject in accordance with RECIST v.1.1 guidelines and the objective response rate presented for each dose cohort. Progression-free survival and durability of response will be determined using Kaplan-Meier methodology.

Objective response, BOR and PFS will be determined and listed for each individual subject. Additionally BOR and PFS will be tabulated. Objective response rate and duration of response will not be calculated.

Section 10.3.3 of the Protocol also states that as a supplement to the standard RECIST v1.1 guidelines established to evaluate anti-tumor responses to chemotherapeutic agents, the sponsor will be analyzing anti-tumor response by assessing total tumor burden over time. Tumor burden activity was not collected and as such no summaries will be included for this data.

Section 10.3.3 of the Protocol also states that at each time point, the change in immunologic response (CTL and Treg frequency in blood) from baseline and from the preceding time point will be correlated with the INXN-1001 dosage level. In addition, tumor punch biopsies or FNAs will be examined for genomic changes due to IL-12 expression, presence of injected adenovirus and CTL frequency, Treg and MDSC frequency, and other immunological markers. The change in each measure from baseline and from the preceding biopsy will be correlated with the INXN-1001 dose used in the each cohort.

Immunologic and biological response marker data will be listed only.

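### The SAP drops the planned objective response rate; the best-response table recovers it only on the activity-evaluable set, and without an interval

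*SAP*

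**What the plan says.** Both documents name ORR in the study rationale. Protocol 5.5 has "The objectives of this Phase I/II clinical trial are to assess the safety, objective response rate, and immunological and biological effects", and SAP 2.0 has "This study was designed to assess the safety, objective response rate and immunological and biological effects". SAP 4.1 makes response the efficacy measure: "Efficacy was to be evaluated as the objective tumor response according to RECIST v1.1 guidelines". The protocol's efficacy analysis (10.3.3) is to have "the objective response rate presented for each dose cohort".

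SAP 11.1.1 defines a responder as a patient with complete response (CR) or partial response (PR). It counts patients who cannot be assessed as non-responders and lists a yes/no response for each subject. It then states "The objective response rate will not be tabulated". SAP 14.0 repeats the decision, "Objective response rate and duration of response will not be calculated", as a change based on the number finally enrolled.

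Several related outputs remain:
- Best overall response (BOR) is listed and tabulated (Table 14.2.1).
- Progression-free survival (PFS) is summarised by Kaplan-Meier median and quartiles (SAP 11.1.2).
- Both tables use the Activity Evaluable population (ACEV), which requires at least one post-screening response evaluation (SAP 8.2).
- Summaries are by phase and dose cohort with an overall column per phase, and inferential statistics are excluded (SAP 9.0).

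**The concern.** A summary that the protocol promised, and that the SAP's own rationale names, is removed for a reason that the total enrolment does not clearly support. SAP 11.1.1 sets up everything needed for the rate and stops one step short.

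What is at stake is how the activity result can be read. The protocol (6.2.6 and 10.1) justified entering additional subjects partly by the wish to estimate the treatment's effect on clinical response, and partly by correlation with immunologic and biologic markers. A reader who rebuilds the rate from the BOR table gets it on a set that depends on having been evaluated after screening, with no statement of how much activity the data can exclude.

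**Working it through.** **1. Patients treated.** SAP 1.0 gives the cohort counts.
- Phase I: 3 + 3 + 3 + 4 = 13.
- Phase II: 4 + 4 + 3 + 2 = 13.
- Total: 26.

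This reproduces SAP 6.1: "Thirteen patients were treated in Phase I and 13 patients were treated in Phase II".

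**2. Against the plan.** The protocol synopsis has 3 subjects in each of 4 cohorts plus about 15 in Phase II, so 4 × 3 + 15 = 27, beside a stated total of approximately 30. Phase I treated 13 against 12, and Phase II 13 against about 15. Protocol 10.1 instead has 6 per cohort, 4 × 6 + 15 = 39, which does not fit its own total of approximately 30. The synopsis components are therefore used here. On that basis the total is one patient short. What changed more is the structure: Phase II was planned at a single dose level and ended as four regimens of 4, 4, 3 and 2.

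**3. What the BOR table gives.** Its categories are CR, PR, stable disease, progressive disease and unevaluable. Under SAP 9.0 and 9.1 it carries counts and percentages by cohort and by phase. So CR% + PR% gives an ORR on ACEV.

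**4. Denominator.** Let x be the responders, N all treated, and n the ACEV size, with n ≤ N. Patients outside ACEV have no post-screening evaluation and would count as non-responders, so the all-treated rate x/N is never above x/n. The ACEV size is not given. As an assumed example, with x = 2 in one phase:
- n = 13: 2/13 = 15.4%.
- n = 12: 2/12 = 16.7%.
- n = 11: 2/11 = 18.2%.

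The all-treated figure stays at 15.4%.

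**5. Precision.** The limits are exact (Clopper-Pearson) 95% limits. For x = 0 the upper limit is 1 − 0.025^(1/n). Otherwise the lower limit is the 2.5% quantile of Beta(x, n − x + 1), and the upper is the 97.5% quantile of Beta(x + 1, n − x). The responder counts below are illustrations.

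| Set | x/n | Rate | Exact 95% limits |
|---|---|---|---|
| One phase | 0/13 | 0% | 0 to 24.7% |
| One phase | 2/13 | 15.4% | 1.9 to 45.4% |
| One phase | 3/13 | 23.1% | 5.0 to 53.8% |
| Both phases | 0/26 | 0% | 0 to 13.2% |
| Both phases | 3/26 | 11.5% | 2.4 to 30.2% |
| Cohort | 0/4 | 0% | 0 to 60.2% |
| Cohort | 0/3 | 0% | 0 to 70.8% |
| Cohort | 0/2 | 0% | 0 to 84.2% |

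The widest possible interval is 55.7 points at 13 patients and 40.2 at 26, but 86.4, 89.8 and 97.4 at 4, 3 and 2.

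**The case against.** The strongest reply is that little is lost. The change is declared in SAP 14.0, as protocol 10.4 provides for. BOR is tabulated with percentages. Best response is also listed on the Safety population (Listing 16.2.6.3), so a careful reader can count responders among all treated patients and compute an interval. ACEV is the protocol's own efficacy set, so the ORR planned in protocol 10.3.3 would have rested on it too. The protocol planned that rate by dose cohort, and cohorts of 2 to 4 give rates that say almost nothing. Read against cohort sizes, the enrolment reason is understandable.

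Most of this stands, and it rules out three stronger readings that a reader might infer:
- **That response gets no estimate at all.** The BOR table supplies one in substance.
- **That dropping ORR removed a planned measure of precision.** The protocol specifies no confidence interval for any endpoint, and the SAP excludes inferential statistics throughout.
- **That ORR is the main secondary endpoint.** The secondary objectives are six and unranked. The relevant one is "To assess preliminary anti-tumor activity according to Response Evaluation Criteria In Solid Tumors (RECIST) 1.1 criteria", which BOR and PFS also serve.

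Two things are not answered. Small cohorts are a reason to omit rates by cohort, which were already weak at the planned 3 patients each, but not to omit a rate by phase. The SAP also keeps PFS medians and quartiles on the same patients, and its default layout would show them by cohort. Being able to count responders from a listing does not replace a stated result with a stated denominator.

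**Conclusion.** The point holds as a gap in reporting. The SAP removes a protocol-planned summary on a ground that fits the split of Phase II but not the total enrolled. What remains is a rate that readers must assemble themselves, on a set that can only match or exceed the all-treated rate, with no interval.

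Per-phase precision is modest but not empty: none in 13 would still put the rate below 24.7%. The pooled figure of 13.2% for none in 26 mixes doses from 5 to 160 mg and daily with every-other-day dosing, so it describes the whole study and no single regimen.

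These figures assume that all 13 or 26 treated patients form the denominator and that the responder counts are hypothetical. The size of the ACEV effect is unknown and could be zero. The primary safety objective is not affected.

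**What to change.** Add ORR rows to Table 14.2.1:
- For each phase, give n/N and a descriptive exact 95% confidence interval, with all treated patients as denominator and unassessable patients as non-responders, in line with SAP 11.1.1.
- Give the same for all 26 pooled, clearly labelled as mixing doses and regimens.
- Show the ACEV rate as supportive, with its n.
- For single cohorts of 2 to 4, show n/N only.

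Reword SAP 11.1.1 and 14.0 to match. State in 14.0 that the interval and the all-treated denominator go beyond what protocol 10.3.3 planned, and in 9.0 that the interval is descriptive and tests no hypothesis.

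The cost is a few table rows, since the yes/no response is already derived for each subject. The price to accept is that the all-treated rate will be equal to or lower than the ACEV rate.
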